# 17 APPENDICES AND ATTACHMENTS

# 17.1 Glossary of Terms

Adverse Device Effect	Adverse event related to the use of an investigational medical device or						
(ADE)	comparator.						
	Note: This definition includes adverse events resulting from insufficient or						
	inadequate instructions for use, deployment, implantation, installation, or						
	operation; any malfunction; and use error or intentional misuse.						
Adverse Event (AE)	Untoward medical occurrence, unintended disease or injury, or untoward clinical signs (including abnormal laboratory findings) in subjects, users or other persons, whether or not related to the investigational medical device or comparator and whether anticipated or unanticipated.  Note: For subjects, this definition includes events related to the						
	investigational medical device, comparator, or the procedures involved.  For users or other persons, this definition is restricted to the use of investigational medical device or comparator.						
Device Deficiency	Inadequacy of a medical device with respect to its identity, quality,						
	durability, reliability, safety, or performance.  Note: This definition includes malfunctions, use errors, and inadequacy in						
	the information supplied by the manufacturer including labelling related						
	to the investigational medical device or the comparator.						
Malfunction	Failure of an investigational medical device to perform in accordance with						
	its intended purpose when used in accordance with the instructions for use						
	or clinical investigation plan (CIP), or Investigator's brochure (IB).						
Nonserious Adverse Event	Adverse event that does not meet the criteria for a serious adverse event.						
Product Complaint	Written, electronic, or oral communication that alleges deficiencies related to the identity, quality, durability, reliability, safety, effectiveness, or performance of a device after it is released for distribution.						
Serious Adverse Device	Adverse device effect that has resulted in any of the consequences						
Effect (SADE)	characteristic of a serious adverse event.						
Serious Adverse Event	Adverse event that led to any of the following:						
Serious Adverse Event (SAE)	• Death.						
	
 
Death.
 
A serious deterioration in the health of the subject, users or other
 
						
	
 
Death.
 
A serious deterioration in the health of the subject, users or other persons as defined by one or more of the following:
 
						
	
 
Death.
 
A serious deterioration in the health of the subject, users or other persons as defined by one or more of the following:
 
a) A life-threatening illness or injury.
 
						
	
 
Death.
 
A serious deterioration in the health of the subject, users or other persons as defined by one or more of the following: 
 
a) A life-threatening illness or injury.
 
 
 
Note: Life-threatening means that the individual was at immediate
 
						
	
 
Death.
 
A serious deterioration in the health of the subject, users or other persons as defined by one or more of the following: 
 
a) A life-threatening illness or injury.
 
 
 
Note: Life-threatening means that the individual was at immediate risk of death from the event as it occurred, i.e., it does not include
 
						
	
 
Death.
 
A serious deterioration in the health of the subject, users or other persons as defined by one or more of the following: 
 
a) A life-threatening illness or injury.
 
 
 
Note: Life-threatening means that the individual was at immediate
 
						
	
 
Death.
 
A serious deterioration in the health of the subject, users or other persons as defined by one or more of the following: 
 
a) A life-threatening illness or injury.
 
 
 
Note: Life-threatening means that the individual was at immediate risk of death from the event as it occurred, i.e., it does not include an event which hypothetically might have caused death had it
 
						
	
 
Death.
 
A serious deterioration in the health of the subject, users or other persons as defined by one or more of the following: 
 
a) A life-threatening illness or injury.
 
 
 
Note: Life-threatening means that the individual was at immediate risk of death from the event as it occurred, i.e., it does not include an event which hypothetically might have caused death had it occurred in a more severe form.
 
b) Any potentially sight-threatening event or permanent impairment to a body structure or a body function including
 
						
	
 
Death.
 
A serious deterioration in the health of the subject, users or other persons as defined by one or more of the following: 
 
a) A life-threatening illness or injury.
 
 
 
Note: Life-threatening means that the individual was at immediate risk of death from the event as it occurred, i.e., it does not include an event which hypothetically might have caused death had it occurred in a more severe form.
 
b) Any potentially sight-threatening event or permanent impairment to a body structure or a body function including chronic diseases.
 
						
	
 
Death.
 
A serious deterioration in the health of the subject, users or other persons as defined by one or more of the following: 
 
a) A life-threatening illness or injury.
 
 
 
Note: Life-threatening means that the individual was at immediate risk of death from the event as it occurred, i.e., it does not include an event which hypothetically might have caused death had it occurred in a more severe form.
 
b) Any potentially sight-threatening event or permanent impairment to a body structure or a body function including
 
						

	· · · · · · · · · · · · · · · · · · ·						
	e) Any indirect harm as a consequence of incorrect diagnostic test results when used within manufacturer's instructions for use.						
	
 
Fetal distress, fetal death, congenital abnormality or birth defect including physical or mental impairment.
 
						
	Note: Planned hospitalization for a preexisting condition, or a procedure required by the CIP, without serious deterioration in health, is not considered a serious adverse event						
Serious Public Health Threat	Signal from any adverse event or device deficiency that indicates an imminent risk of death, serious deterioration in state of health or a serious deterioration in the health in subjects, users or other persons, and that requires prompt remedial action for other subjects, users or other persons. Note: This would include events that are of significant and unexpected nature such that they become alarming as a potential serious health hazard or possibility of multiple deaths occurring at short intervals.						
Use Error	User action or lack of user action while using the medical device that leads to a different result than that intended by the manufacturer or expected by the user.  Note:  a) Use error includes the inability of the user to complete a task.  b) Use errors can result from a mismatch between the characteristics of the user, user interface, task or use environment.						
	
 
c) Users might be aware or unaware that a use error has occurred.
 
d) An unexpected physiological response of the patient is not by itself considered a use error.
 
e) A malfunction of a medical device that causes an unexpected result is not considered a use error.
 
						

# 17.2 Patient Questionnaires

# 17.2.1 IDEEL-SB Questionnaire

# Symptom Bother

These questions ask about the symptoms you may experience due to dry eyes.

#### 1. OVER THE LAST TWO WEEKS, how often did you experience dry eye symptoms?

None of the time	A little of the time	Some of the time	Most of the time	All of the time

The following questions ask about how bothersome dry eye symptoms were to you OVER THE
LAST TWO WEEKS. If you had the symptom, please choose **how much the symptom bothered you** (not at all, slightly, moderately, or very much). If you did not have the symptom over the last week, choose the "I did not have this symptom / Not applicable" box. Please choose only one box per question.

			OVER THE LAST TWO WEEKS, I had this symptom and it bothered me:			
of th	ER THE LAST TWO EKS, how much did each ne following symptoms ner you?	I did not have this symptom / Not applicable	Not at all	Slightly	Moderately	Very much
2.	Eyes that felt gritty or sandy					
3.	Felt like I needed to close my eyes even though I was not tired		0	0	0	0
4.	Burning or stinging eyes					
5.	Tired eyes					
6.	Blurry vision					
7.	Itchy eyes					
8.	Irritated eyes					
9.	Eyes that felt like they had been scratched by something					
10.	Eye dryness					

Copyright © 2002, Alcon Laboratories

		OVER THE LAST TWO WEEKS, I had this symptom and it bothered me:			
OVER THE LAST TWO WEEKS, how much did each of the following symptoms bother you?	I did not have this symptom / Not applicable	Not at all	Slightly	Moderately	Very much

 
Mucus in, around, or coming out of my eyes
 
					0
12. Puffy or swollen eyes					
13. Eye redness	0			0	
14. Aching or sore eyes		0			

 
Felt like something was in my eye
 
	0			0	0

 
Frequent and/or rapid blinking
 
				0	
Difficulty blinking because of little or no moisture in my eyes	0	0	0	0	0

 
Sensitivity to light, glare, and/or wind
 
	0				
Sensitivity to re- circulated air (such as air conditioning and heat)	0	0	0	0	0
Headaches associated with dry eye symptoms					

Thank you for finishing this questionnaire. Please make sure that you answered every question.

Copyright © 2002, Alcon Laboratories

# **List of Abbreviations**

Abbreviation	Description
AE	Adverse Event
BCVA	Best Corrected Visual Acuity
CI	Confidence Interval
CSR	Clinical Study Report
DE	Dry Eye
DED	Dry Eye Disease
DES	Dry Eye Symptoms
DEWS	Dry Eye Workshop
IC	Informed Consent
IDEEL-SB	Impact of Dry Eye on Everyday Life - Symptom Bother
FAS	Full Analysis Set Population
MedDRA	Medical Dictionary for Regulatory Activities
OD	Oculus Dexter/Right Eye
OS	Oculus Sinister/Left Eye
PMCF	Post-Market Clinical Follow-Up
PF	Preservative Free
PP	Per-Protocol Population
PT	Preferred Term
Q1	First Quartile, 25th Percentile
Q3	Third Quartile, 75th Percentile
SAE	Serious Adverse Event
SAP	Statistical Analysis Plan
SD	Standard Deviation
TEAE	Treatment-Emergent Adverse Event
TFOS	Tear Film and Ocular Surface Society
VA	Visual Acuity
US	United States

## 1. Study Objectives and Design

#### 1.1. Introduction

The purpose of this statistical analysis plan (SAP) is to describe in detail the statistical methodology and planned analyses ICON plc will conduct as a part of Alcon's Protocol DEC262-I001 for inclusion in the Clinical Study Report (CSR). The content of this SAP is based on Protocol V1.0 dated 24 April 2023. ICON plc will document any small deviations from the analyses outlined in this plan with rationale in the final CSR. Any major changes to the conduct of the study will be recorded in a protocol amendment and SAP change log.

ICON PLC will perform the statistical analyses and is responsible for the production and quality control of all tables, listings and figures.

This post-market clinical follow-up (PMCF) study aims to assess the performance and safety of Systane Complete Preservative Free (PF) Lubricant Eye Drops in adult subjects (≥ 18 years) experiencing mild to moderate dry eye disease (DED) outside the United States (US), where the product is commercially available.

# 1.2. Study Objectives

#### PRIMARY OBJECTIVE:

The primary objective of this PMCF study is to assess the performance and safety of Systane Complete PF Lubricant Eye Drops in subjects experiencing dry eye symptoms (DES).

[figure not shown]
# 1.3. Study Descriptions

#### 1.3.1. Overview of Study Design

This is a post-market, multicenter, non-comparative, single arm, open-label, prospective clinical study to assess the performance and safety of Systane Complete PF Lubricant Eye Drops in adult subjects experiencing DES.

The study will be conducted outside the US, where the product is commercially available, in clinical sites known to routinely manage subjects with DED.

[figure not shown]
Figure 1: Overall Study Design.

Systane Complete PF will be dispensed at Screening/Baseline visit. Subjects will be expected to attend one additional visit at Day 30 (±2days) after screening and a telephone call visit at Day 15 (±2days).

Eligible subjects will initiate treatment with Systane Complete PF. On Day 1, eligible subjects will be asked to instill one drop of Systane Complete PF in each eye on-site (during the Screening/Baseline visit) and the subsequent drop only after 8 hours (± 1 hour) at home. For the rest of the study duration (up to Visit 3), subjects will be asked to self-administer 1-2 drops in each eye; four times a day. The dose selected in this study is the dose approved for Systane Complete PF for the management of DED (Figure 2).

Figure 2: Systane Complete PF Dose Regimen.

As shown in Figure 1, subjects will participate in the study for approximately 30 days, with a phone call scheduled on Day  $15 \pm 2$  (Visit 2) and a follow-up visit scheduled on Day  $30 \pm 2$  (Visit 3). Subjects may have unscheduled visits if deemed necessary per the Investigator's judgment.

Subjects will be asked to complete subject questionnaires on Day 1 (Impact of Dry Eye on Everyday Life - Symptom Bother [IDEEL-SB] and at Visit 3 (IDEEL-SB). In addition, subjects will be instructed to document Systane Complete PF dosing information on a daily basis using a subject diary.

The overall study duration (first subject screened to last subject's final study visit) is expected to be approximately 2 months.

The schedule of study assessments is presented in Table 1.

Table 1: Data Collection Schedule

Procedure/Assessment	Visit 1 Screening/ Baseline (Day 1)	Visit 2 (phone) 15-day Follow-up (±2 days)	Visit 3 30-day / Exit (±2 days)	Unscheduled Visit / Early Exit
Informed consent (IC)	X			
Demographics	X	]		
Targeted medical history	X			
Targeted concomitant medications	X			
IDEEL-SB questionnaire	X		X	(X)
Inclusion/Exclusion	X			
Changes in concomitant medications		X	X	X
Best Corrected Visual Acuity (BCVA)	X		X	(X)
Biomicroscopy (include corneal staining)	X		X	(X)
Adverse events (AEs)	X	X	X	X
Device deficiencies	X	X	X	X
Exit form	(X)		X	X
Telephone follow-up for compliance check		X		

X) assessment performed as necessary

#### 1.3.2. Study Population

The study population consists of adult male and female subjects (≥18 years) with mild to moderate DED. Subjects will be selected based on the inclusion criteria and exclusion criteria listed in Sections 6.4.4 and 6.4.5 of the protocol.

#### 1.4. Randomization

Randomization is not applicable for this study.

<sup>a On Day 1: before Systane Complete PF first dose, immediately after first dose, and 8 hours after first dose (prior to administering evening dose of Systane Complete PF)

## 1.5. Masking

This study is open-label.

#### 1.6. Interim Analysis

No interim analyses are planned.

## 2. Analysis Sets

Two analysis sets will be defined for this study as outlined below.

#### 2.1. Full Analysis Set (FAS)

The FAS will include all subjects/eyes exposed to at least one dose of Systane Complete PF. The FAS will be the primary analysis set for all effectiveness and safety analyses.

## 2.2. Per-Protocol (PP)

The PP is a subset of the FAS and will exclude subjects with major protocol deviations. The PP population will be used as a supportive set for primary effectiveness analyses if the protocol deviation subjects exceed 5%. Major protocol deviations leading to the exclusion from PP population will be identified in the "Protocol Deviation Criteria Form".

# 3. General Aspects for Statistical Analysis

#### 3.1. General Methods

In general, summaries will present data overall and by DED groups (aqueous deficient DE, evaporative DE, and mixed DE).

No hypothesis testing will be performed. Whenever applicable, 95% confidence intervals (CIs) will be provided. For proportions, 95% CIs will be calculated using the exact Binomial (Clopper-Pearson) method [1]. 95% CIs of a normal distribution for means will be provided, as needed.

All relevant subject data will be included in listings. The listings will be sorted by subject ID, and other characteristics (age, sex, eye(s), etc.), if necessary.

Data collected for IDEEL-SB, BCVA, and Biomicroscopy findings at unscheduled visits may be included in by-visit summaries and analyzed in the same fashion as the data collected at scheduled visits except where otherwise noted.

SAS® version 9.4 or higher will be used for all statistical analyses and tabulations.

## 3.2. Rules for Reporting Statistics

Continuous variables will be summarized using descriptive statistics, i.e., by the number of non-missing observations (n), mean, standard deviation (SD), first quartile (Q1), median, third quartile (Q3), minimum and maximum. Where specified in the table shells, the number of missing observations and 95% CI for the mean will also be provided.

#### For reporting conventions:

- The number of non-missing and missing observations will be presented as whole numbers.
- The minimum and maximum will be presented with the same number of decimal places as presented in the data.
- The mean (and correspondent 95% CI), median, Q1 and Q3 will generally be displayed with one more decimal place than presented in the data.
- The SD will generally be displayed with 2 more decimal places than the raw data. If there is only one observation (n=1), the SD will be displayed as a hyphen ("-").
- If there is no observation, summary statistics will be displayed with a hyphen ("-").

Qualitative variables will be summarized by frequency counts (n) and percentages (%). Unless otherwise stated, the calculation of proportions/percentages for a given qualitative variable will exclude subjects/eyes with missing values from the denominator.

For reporting conventions, percentages will be reported to one decimal place unless greater precision is deemed appropriate, except for cases when 100% is presented. In cases of a count of 0, the percentage will not be presented.

In case the analysis refers only to certain visits/timepoints, summary statistics and percentages will be based on the number of subjects/eyes having available result at each visit/timepoint. Summaries on change from Baseline by visit/timepoint will be based on subjects/eyes who have both baseline and post-baseline values at the visit/timepoint being summarized.

#### 3.3. Key Definitions

**Enrolled subjects** are defined as all subjects who provided signed IC.

**Eligible subjects** are defined as all subjects who provided signed IC and met all the eligibility criteria for this study.

**Baseline** is defined as the last non-missing value prior to the start date of the study treatment. For non-treated subjects, baseline is defined as the value from the Visit 1 (Screening).

**Study Day 1** is defined as the first day of study treatment administration. Study day will be calculated as date of event/collection – first dose date of the study treatment + 1 for all assessments after start of study treatment and as date of event/collection – first dose date of the study treatment for all assessments prior to start of study device use.

End of study date is defined as the date of the latest of the following events:

- Date of early termination collected from the "Subject Disposition" eCRF form (not use if reason for discontinuation is lost to follow-up).
- Last contact date among the following dates (only completed dates) collected on the eCRF:
  - o Subject assessment dates (e.g., IDEEL-SB questionnaire, slit lamp biomicroscopy, BCVA.
  - o AE start and end dates.
  - o Device deficiency dates.
  - o Visit dates (only performed visits).
  - o Study treatment start and end dates.

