# 3.5. Analysis Visit Windows

As per the protocol, data will be collected for the assessments at the Screening/Baseline (Visit 1), 15-day Follow-up (Visit 2), and 30-day/Exit (Visit 3). The data will be collected within  $\pm 2$ 

days window for the Visit 2 and Visit 3. By-visit summaries will use the analysis visit. Scheduled, unscheduled and early termination visits will be windowed based on the following analysis visit window (Table 2).

- 1) If the scheduled records do not fall within a visit window, then the records will be flagged as out of the allowed window and the original visit from the eCRF will be assigned for the analysis visit. In case of unscheduled records not falling within a visit window, the original visit from the eCRF will be assigned.
- 2) For post-baseline visits, if there is more than 1 record available within the same visit window, the following rules will be applied:
  - a. Select the record collected at the scheduled visit.
  - b. If there are no records at the scheduled visit, then the record closest to the target day will be used.
  - c. If there are multiple records with the same distance to the target day, the latest record will be used.
- For Baseline visit, the last non-missing record among scheduled and unscheduled assessments will be selected.

Table 2: Analysis Visit Window

Analysis	Target Study	Visit Window for , IDEEL-SB, BCVA,	
Visit	Day	Biomicroscopy	
Baseline	1	<=1	
Visit 2	15	13 to 17	
Visit 3	30	28 to 32	

In general, only observations assigned to an analysis visit window will be included in the analysis. Data collected at unscheduled visits will be included in the data listings. In addition, any data collected out of the allowed window will be flagged in the listings.

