# 4.3. Demographics and Clinical Characteristics at Baseline

Analysis Set: FAS

Demographic and clinical characteristics at Baseline will be summarized using the information collected from the screening data. Demographic characteristics will include:

- Age (years).
- Age categories: >=18 years to <30 years, >=30 years to <50 years, >=50 years to <70 years and >=70 years.
- Sex: Male, Female, Unknown, Unconfirmed.
- Race: American Indian or Alaska Native, Asian, Black or African American, Native Hawaiian or other Pacific Islander, White, Other, Unknown, Unconfirmed.
  - Note: An additional category "Mixed" will be created for subjects with more than one race reported.
- Ethnicity: Hispanic or Latino, Not Hispanic or Latino, Unknown, Unconfirmed.
- IDEEL-SB symptoms score.
- \_
- BCVA score (logMAR) [eye-level summary].

A supportive listing for demographic and clinical characteristics will be provided.

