# 5.3. Statistical Methods for Efficacy Analyses

#### 5.3.1. Primary Effectiveness

[figure not shown]
DES will be assessed using the IDEEL-SB questionnaire (see Appendix 13.2) at the Screening/Baseline visit (Day 1) before Systane Complete PF use, and at Visit 3 (and at unscheduled and at early exit visits, as necessary).

The primary effectiveness endpoint is the IDEEL-SB score. The IDEEL-SB score is calculated by the mean value of the non-missing item scores multiplied by 25

The primary effectiveness endpoint will be summarized as a continuous variable at each analysis visit (Baseline and Visit 3). The mean IDEEL-SB score will be presented together with the corresponding 95% CI. In addition, the change from Baseline will be summarized at Visit 3.

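### The SAP 3.3 baseline definition cuts at the treatment start date, which is the Visit 1 date, and conflicts with the day <=1 rule in SAP 3.5; both should say before the first dose

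*SAP*

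**What the plan says.** The SAP has two rules for choosing the baseline record.

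- **SAP 3.3 (Key Definitions).** Baseline is "defined as the last non-missing value prior to the start date of the study treatment". The only fallback reads: "For non-treated subjects, baseline is defined as the value from the Visit 1 (Screening").
- **SAP 3.5 (Analysis Visit Windows).** Table 2 sets the Baseline window at study day <=1, with target day 1. The selection rule is: "For Baseline visit, the last non-missing record among scheduled and unscheduled assessments will be selected". Neither requires the record to precede the first dose. For post-baseline visits with several records in a window, the first rule is "Select the record collected at the scheduled visit"; the Baseline bullet gives no such priority.

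Four other places bear on which rule can work:

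- SAP 1.3.1 and protocol 6.1 have eligible subjects instill "one drop of Systane Complete PF in each eye on-site (during the Screening/Baseline visit") on Day 1.
- SAP 2.1: "The FAS will include all subjects/eyes exposed to at least one dose of Systane Complete PF".
- SAP 4.3 says that demographic and "clinical characteristics at Baseline will be summarized using the information collected from the screening data".
- SAP 5.3.1 has IDEEL-SB completed at the "Screening/Baseline visit (Day 1) before Systane Complete PF use, and at Visit 3". Protocol 7.3.3.1 agrees.

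**The concern.** Screening, baseline assessment and first dose share one visit and one date. A definition that requires a value from before the start date cannot be met by anything recorded at that visit. The window rule has the opposite weakness: it accepts any record from that date, before or after the drop, and takes the last.

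Baseline is the reference for the IDEEL-SB change from baseline (the primary endpoint), the BCVA change from baseline and the biomicroscopy shift tables. SAP 3.2 limits change-from-baseline summaries to subjects or eyes with both a baseline and a post-baseline value. SAP 9 calls for checks on derived variables; a check against 3.3 and a check against 3.5 would disagree on the same record. Protocol 9.7.1 lists blurred vision and eye redness among the product's possible effects, so a post-dose BCVA or hyperemia grade would not be a neutral reference value.

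**Working it through.** No figure in the plan depends on this definition, so there is none to reproduce. The check applies each rule to one treated subject.

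**Inputs**
- *d* = date of first dose = date of Visit 1 (SAP 1.3.1, protocol 6.1).
- Measures visible in SAP Table 1 and protocol Table 4 with a scheduled Visit 1 record: IDEEL-SB, BCVA and biomicroscopy, so three, with one record each.
- Study day (SAP 3.3): date − *d* + 1 for assessments after the start of treatment; date − *d* for assessments before it.

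**Step 1. SAP 3.3 as written.** A record qualifies if its date < *d*. For a Visit 1 record this is *d* < *d*, which is false, so 0 of 3 scheduled records qualify. The fallback does not help, because a non-treated subject has had no dose and so is not in the FAS.

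**Step 2. SAP 3.5 and Table 2.** A record qualifies if its study day is <=1.
- Same-day pre-dose record: *d* − *d* = 0, which qualifies.
- Same-day post-dose record: *d* − *d* + 1 = 1, which qualifies.

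So 3 of 3 scheduled records qualify, wherever in the visit they were taken. With one record per measure, the last non-missing record is the scheduled one.

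**Step 3. Add a same-day post-dose unscheduled record.** This record is hypothetical; the schedule has none for these measures. Unscheduled visits are allowed at the investigator's judgment, and SAP 3.1 lets their IDEEL-SB, BCVA and biomicroscopy data enter by-visit summaries.

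| Rule | Scheduled pre-dose record | Extra post-dose record | Selected |
|---|---|---|---|
| SAP 3.3 as written | does not qualify | does not qualify | none |
| SAP 3.5 / Table 2 | qualifies (day 0) | qualifies (day 1) | post-dose record |
| Before first dose | qualifies | does not qualify | pre-dose record |

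**Step 4. Stated order at Visit 1.** The visible text places the scheduled measure before the drop for 1 of 3 (IDEEL-SB). For the other two, protocol 7.3.4.2 and 7.3.4.3 and SAP 6.3.2 and 6.3.3 give the visit but not the order relative to the drop.

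**The case against.** The strongest reply is that nobody would misapply this. Table 2, SAP 4.3 and SAP 5.3.1 all place Baseline at Visit 1. The study-day rule in SAP 3.3 itself separates assessments before and after the start of treatment, so its authors had the event in mind as well as the date. IDEEL-SB is expressly collected before use. That stands, and it is why the point is minor. It does not remove the conflict: the key definition, followed as written, fails for this design, and the rule that does work lacks the pre-dose condition.

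Three stronger readings are tempting, and the documents do not support them.

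- A reader might infer that the change-from-baseline tables will be empty. That follows only if SAP 3.3 is applied literally and Table 2, SAP 4.3 and SAP 5.3.1 are ignored.
- A reader might infer that Visit 1 BCVA and biomicroscopy are done after the drop, or that the plan leaves their order open. The supportable statement is only that the visible text does not give the order. The design and dose-regimen figures are not shown, and they might give it.
- A reader might take footnote a of the schedule, which sets assessments before, immediately after and 8 hours after the first dose on Day 1, as proof that post-dose records of these measures exist. The row that the footnote belongs to is not visible, so nothing is claimed about that measure.

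The exposure in Step 3 is also hypothetical: the documents give no expected number of such records. For IDEEL-SB, with its two-week recall period, a same-day repeat would have little purpose.

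**Conclusion.** The concern holds as a minor specification error. SAP 3.3 states a rule that 0 of 3 visible scheduled Visit 1 measures can meet in a treated subject. SAP 3.5 states a different rule that 3 of 3 meet, but without a pre-dose condition or priority for the scheduled record. The intended value is clearly the pre-dose Visit 1 value.

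No loss of data and no size of bias is claimed, and no sample size or precision figure changes. The conclusion rests on Visit 1 and the first dose sharing a date, which both documents state. The risk of selecting a post-dose record rests on an extra same-day record existing, which is an assumption. Whether Visit 1 BCVA and biomicroscopy precede the drop remains a question for the sponsor, not a finding.

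**What to change.** Change the SAP only:

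1. In SAP 3.3, replace the start-date condition with *before the first dose of study treatment*.
2. In the SAP 3.5 baseline bullet and the Table 2 Baseline row, use *Day <=1 and before the first dose*.
3. Where assessment times are not collected, use the scheduled Visit 1 record as baseline. Flag in the listings any value known or suspected to be post-dose, without excluding it. Excluding values for lack of documented timing would remove baselines that Table 2 now supplies.

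Separately, the sponsor should confirm from the full documents whether Visit 1 BCVA and biomicroscopy precede the first drop.

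The cost is one phrase, one bullet, one table cell and a short rule for missing times, issued as a new SAP version under SAP 9, plus a listing flag. No new endpoint data are needed. If the Visit 1 procedures themselves had to change, that would go through the amendment process in protocol Section 12, with IRB/IEC approval before implementation. The study-day formula, which gives a same-day pre-dose record day 0 against a target of day 1, can be tidied in the same edit; it does not affect window assignment.
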